## 6.5.2 Rescue Medications and Supportive Care

Participants should receive appropriate supportive care measures as deemed necessary by the treating investigator. Suggested supportive care measures for the management of AEs with potential immunologic etiology are outlined along with the dose modification guidelines in Section 6.6, [Table 4](#). Where appropriate, these guidelines include the use of oral or IV treatment with corticosteroids, as well as additional antiinflammatory agents if symptoms do not improve with administration of corticosteroids. Note that several courses of steroid tapering may be necessary as symptoms may worsen when the steroid dose is decreased. For each disorder, attempts should be made to rule out other causes such as metastatic disease or bacterial or viral infection, which might require additional supportive care. The treatment guidelines are intended to be applied when the Investigator determines the events to be related to pembrolizumab.

Note: If after the evaluation of the event, it is determined not to be related to pembrolizumab, the Investigator does not need to follow the treatment guidance. Refer to Section 6.6 for guidelines regarding dose modification and supportive care.

It may be necessary to perform conditional procedures such as bronchoscopy, endoscopy, or skin photography as part of evaluation of the event.

## 6.6 Immune-related Events and Dose Modification (Withhold, Treat, Discontinue)

### **Dose Modification and Toxicity Management for Immune-related AEs Associated with Pembrolizumab**

AEs associated with pembrolizumab exposure may represent an immune-related response. These irAEs may occur shortly after the first dose or several months after the last dose of pembrolizumab treatment and may affect more than one body system simultaneously. Therefore, early recognition and initiation of treatment is critical to reduce complications. Based on existing clinical study data, most irAEs were reversible and could be managed with interruptions of pembrolizumab, administration of corticosteroids and/or other supportive care. For suspected irAEs, ensure adequate evaluation to confirm etiology or exclude other causes. Additional procedures or tests such as bronchoscopy, endoscopy, skin biopsy may be included as part of the evaluation. Based on the severity of irAEs, withhold or permanently discontinue pembrolizumab and administer corticosteroids.

Dose Modification and Toxicity Management Guidelines for irAEs associated with pembrolizumab monotherapy, coformulations, or IO combinations are provided in [Table 4](#).

**Table 4 Dose Modification and Toxicity Management Guidelines for Immune-related Adverse Events Associated with Pembrolizumab Monotherapy, Coformulations or IO Combinations**

General instructions:				

 
1. Severe and life-threatening irAEs should be treated with IV corticosteroids followed by oral steroids. Other immunosuppressive treatment should begin if the irAEs are not controlled by corticosteroids.
 
2. Pembrolizumab monotherapy, coformulations or IO combinations must be permanently discontinued if the irAE does not resolve or the corticosteroid dose is not <math>\leq 10</math> mg/day within 12 weeks of the last treatment.
 
3. The corticosteroid taper should begin when the irAE is <math>\leq</math> Grade 1 and continue at least 4 weeks.
 
4. If pembrolizumab monotherapy, coformulations or IO combinations have been withheld, treatment may resume after the irAE decreased to <math>\leq</math> Grade 1 after corticosteroid taper.
 
				
irAEs	Toxicity Grade (CTCAEv4.0)	Action With Pembrolizumab Monotherapy, Coformulations or IO Combinations	Corticosteroid and/or Other Therapies	Monitoring and Follow-up
Pneumonitis	Grade 2	Withhold	
 
• Administer corticosteroids (initial dose of 1-2 mg/kg prednisone or equivalent) followed by taper
 
	
 
• Monitor participants for signs and symptoms of pneumonitis
 
• Evaluate participants with suspected pneumonitis with radiographic imaging and initiate corticosteroid treatment
 
• Add prophylactic antibiotics for opportunistic infections
 

	Recurrent Grade 2 or Grade 3 or 4	Permanently discontinue		
Diarrhea / Colitis	Grade 2 or 3	Withhold	
 
• Administer corticosteroids (initial dose of 1-2 mg/kg prednisone or equivalent) followed by taper
 
	
 
• Monitor participants for signs and symptoms of enterocolitis (ie, diarrhea, abdominal pain, blood or mucus in stool with or without fever) and of bowel perforation (ie, peritoneal signs and ileus)
 
• Participants with <math>\geq</math>Grade 2 diarrhea suspecting colitis should consider GI consultation and performing endoscopy to rule out colitis
 
• Participants with diarrhea/colitis should be advised to drink liberal quantities of clear fluids. If sufficient oral fluid intake is not feasible, fluid and electrolytes should be substituted via IV infusion.
 

	Recurrent Grade 3 or Grade 4	Permanently discontinue		

irAEs	Toxicity Grade (CTCAEv4.0)	Action With Pembrolizumab Monotherapy, Coformulations or IO Combinations	Corticosteroid and/or Other Therapies	Monitoring and Follow-up
AST / ALT Elevation or Increased Bilirubin	Grade 2	Withhold	
 
Administer corticosteroids (initial dose of 0.5-1 mg/kg prednisone or equivalent) followed by taper
 
	
 
Monitor with liver function tests (consider weekly or more frequently until liver enzyme value returned to baseline or is stable)
 

	Grade 3 or 4	Permanently discontinue	
 
Administer corticosteroids (initial dose of 1-2 mg/kg prednisone or equivalent) followed by taper
 
	
T1DM or Hyperglycemia	New onset T1DM or Grade 3 or 4 hyperglycemia associated with evidence of $\beta$ -cell failure	Withhold a	
 
Initiate insulin replacement therapy for participants with T1DM
 
Administer anti-hyperglycemic in participants with hyperglycemia
 
	
 
Monitor participants for hyperglycemia or other signs and symptoms of diabetes
 

Hypophysitis	Grade 2	Withhold	
 
Administer corticosteroids and initiate hormonal replacements as clinically indicated
 
	
 
Monitor for signs and symptoms of hypophysitis (including hypopituitarism and adrenal insufficiency)
 

	Grade 3 or 4	Withhold or permanently discontinue a		
Hyperthyroidism	Grade 2	Continue	
 
Treat with non-selective beta-blockers (eg, propranolol) or thionamides as appropriate
 
	
 
Monitor for signs and symptoms of thyroid disorders
 

	Grade 3 or 4	Withhold or Permanently discontinue a		

irAEs	Toxicity Grade (CTCAEv4.0)	Action With Pembrolizumab Monotherapy, Coformulations or IO Combinations	Corticosteroid and/or Other Therapies	Monitoring and Follow-up
Hypothyroidism	Grade 2-4	Continue	
 
Initiate thyroid replacement hormones (eg, levothyroxine or liothyronine) per standard of care
 
	
 
Monitor for signs and symptoms of thyroid disorders
 

Nephritis and renal dysfunction	Grade 2	Withhold	
 
Administer corticosteroids (prednisone 1-2 mg/kg or equivalent) followed by taper
 
	
 
Monitor changes of renal function
 

	Grade 3 or 4	Permanently discontinue		
Myocarditis	Grade 1	Withhold	
 
Based on severity of AE administer corticosteroids
 
	
 
Ensure adequate evaluation to confirm etiology and/or exclude other causes
 

	Grade 2, 3 or 4	Permanently discontinue		
All Other irAEs	Persistent Grade 2	Withhold	
 
Based on severity of AE administer corticosteroids
 
	
 
Ensure adequate evaluation to confirm etiology or exclude other causes
 

	Grade 3	Withhold or discontinue b		
	Recurrent Grade 3 or Grade 4	Permanently discontinue		

AE(s)=adverse event(s); ALT= alanine aminotransferase; AST=aspartate aminotransferase; CTCAE=Common Terminology Criteria for Adverse Events; DRESS=Drug Rash with Eosinophilia and Systemic Symptom; GI=gastrointestinal; IO=immuno-oncology; ir=immune related; IV=intravenous; SJS=Stevens-Johnson Syndrome; T1DM=type 1 diabetes mellitus; TEN=Toxic Epidermal Necrolysis; ULN=upper limit of normal.
 
Note: Non-irAE will be managed as appropriate, following clinical practice recommendations.
 
a The decision to withhold or permanently discontinue pembrolizumab monotherapy, coformulations or IO combinations is at the discretion of the investigator or treating physician. If control achieved or ≤ Grade 2, pembrolizumab monotherapy, coformulations or IO combinations may be resumed.
 
b Events that require discontinuation include, but are not limited to: Guillain-Barre Syndrome, encephalitis, myelitis, DRESS, SJS, TEN and other clinically important irAEs (eg, vasculitis and sclerosing cholangitis).
				

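### Protocol Table 4 gives two restart grades with no stated precedence; for hypophysitis, an event that began at Grade 3-4 may be dosed at Grade 2 while one first graded 2 is withheld

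*Protocol*

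**What the plan says.** All of the text is in Protocol Section 6.6, Table 4.

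- **General instruction 4** covers any withheld treatment: "treatment may resume after the irAE decreased to" Grade 1 or less, with the further condition that this comes after the corticosteroid taper ("Grade 1 after corticosteroid taper").
- **General instruction 3** governs the taper. It starts once the event is at Grade 1 or less, and it must run on: "and continue at least 4 weeks".
- **Footnote a** leaves the choice between withholding and stopping to the investigator or treating physician, then adds: "If control achieved or ≤ Grade 2, pembrolizumab monotherapy, coformulations or IO combinations may be resumed". It is marked on three entries only: T1DM/hyperglycemia, Grade 3-4 hypophysitis and Grade 3-4 hyperthyroidism.
- **Hypophysitis rows.** The lower-grade entry reads "Hypophysitis Grade 2 Withhold" and carries no footnote. The Grade 3 or 4 entry reads "Withhold or permanently discontinue" and carries footnote a.
- **Hyperthyroidism rows.** Grade 2 is Continue; Grade 3 or 4 carries footnote a.
- **Myocarditis rows.** Grade 1 is withheld without a footnote, and Grades 2 to 4 are permanently discontinued. Corticosteroids depend on how severe the event is.

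Neither instruction 4 nor footnote a refers to the other.

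**The concern.** A dose-modification table should give one answer for a given event at a given grade. Here one line permits restart at Grade 2 and two others point to holding. In hypophysitis the permissive line applies to the events that were worse to begin with, and a severity-graded table would normally be ordered the other way.

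Participants in Part 1 have no evidence of disease at entry, so a decision to re-expose them after an immune-related event should not depend on which line of a table the site happens to read. A site that resumes at Grade 2 cannot tell whether it has followed the protocol or deviated from it. The same decisions feed dose modification and discontinuation due to an AE, which are Tier 2 safety endpoints in SAP Section 3.6.2 (Table 5).

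**Working it through.** No arithmetic applies. The check compares, row by row, the grade at which drug is withheld with the grade at which it may be resumed.

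| Entry | Action in the row | Footnote a? | Restart under instruction 4 | Restart under footnote a | Result |
|---|---|---|---|---|---|
| Hypophysitis, Grade 3-4 | Withhold or stop | Yes | Grade 1 or less, after taper | Control, or Grade 2 or less | Conflicts with instruction 4 and with the Grade 2 row |
| Hypophysitis, Grade 2 | Withhold | No | Grade 1 or less, after taper | Not applicable | Instruction 4 alone |
| Hyperthyroidism, Grade 3-4 | Withhold or stop | Yes | Grade 1 or less, after taper | Control, or Grade 2 or less | Agrees with the Grade 2 row (Continue); differs from instruction 4 only |
| T1DM/hyperglycemia | Withhold | Yes | Grade 1 or less, after taper | Control, or Grade 2 or less | No Grade 2 row; differs from instruction 4 only |
| Myocarditis, Grade 1 | Withhold | No | Grade 1 or less, after taper | Not applicable | Grade part already met at onset |

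**Hypophysitis.** Take two participants who are both at Grade 2 today.

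1. Participant A began at Grade 3 and has improved to Grade 2. Footnote a allows dosing. Instruction 4 does not, because Grade 2 is above Grade 1.
2. Participant B was first graded 2. The row says to withhold, no footnote applies, and restart needs Grade 1 or less after the taper. By instruction 3 the taper begins only at Grade 1 or less and lasts at least 4 weeks.

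If the rows are read by current grade, participant A falls in the Grade 2 row and is withheld, while the footnote on the row of origin permits dosing. If the rows are read by the grade at which the event began, A may be dosed and B may not. One reading gives a contradiction and the other an inverted order of strictness. Neither is free of the problem.

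This uses only the grade limb of footnote a. The alternative limb, that control has been reached, has no grade attached and is not needed for the argument.

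**Myocarditis.** A Grade 1 event satisfies the grade part of instruction 4 when it appears. Two further elements remain: the event must have decreased, and a taper must have taken place. If steroids are given, the taper clause still delays restart. If they are not, which the row allows, there is no taper, and the grade criterion cannot separate the state in which drug is held from the state in which it may be resumed.

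**The case against.** The best answer is that footnote a is a row-specific exception. Instruction 4 stands in a list headed as general, and a superscript on named rows is ordinarily read as overriding such a list. The T1DM and hyperthyroidism rows prescribe no corticosteroids, so a restart rule tied to a taper does not fit them and the footnote fills the space. In hyperthyroidism it also agrees with the Grade 2 row. Most of this stands, and a precedence sentence would settle those two entries. It does not settle hypophysitis, where corticosteroids are listed and the Grade 2 row still says to withhold.

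It can also be said that footnote a is permissive, so a site that goes on holding breaches nothing, and that some variation between investigators is intended. That is fair. The defect is that the table does not say whether resuming at Grade 2 is allowed.

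Amendment 4 revised the table to align with the US prescribing information. That explains its origin but supplies no rule of precedence.

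A reader might infer more than the text supports:

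- **That Table 4 contradicts itself generally.** It does not. Footnote a covers three entries, and the clash between rows is confined to hypophysitis.
- **That Grade 1 myocarditis may be dosed at onset.** The row says to withhold, and instruction 4 also requires a decrease and a taper. This is a gap, not a contradiction, and footnote a plays no part in it.
- **That all myocarditis events are affected.** Grades 2 to 4 are permanently discontinued and have no restart decision.
- **That Part 2 access turns on this.** A temporary hold does not in itself prevent completion of 17 cycles, and Protocol Section 6.7 refers non-completion to the Sponsor for a decision on eligibility.

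**Conclusion.** The point holds in a narrow form. Instruction 4 and footnote a give different restart grades with no stated precedence. In hypophysitis this leaves an event that has come down from Grade 3-4 with a more lenient restart rule than one first graded 2, even if the footnote is accepted as an exception. Grade 1 myocarditis managed without steroids is a minor related gap.

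The size cannot be given as a count. The documents contain no rates for these events, and a figure obtained by assuming one would mostly count events for which a single rule is clear. The effect on the analysis is limited: the Tier 2 confidence intervals are descriptive, and neither the RFS, DMFS or OS tests nor the power depend on this table. The reason to act is participant safety and consistent conduct across sites. The conclusion rests on the table as printed and on no view of which threshold is clinically right.

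**What to change.** The sponsor should:

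1. reconcile general instruction 4, footnote a and the two hypophysitis rows, so that a participant at Grade 2 has one answer whatever the starting grade, or state that the difference is intended;
2. state whether footnote a overrides the general instructions for the rows that carry it;
3. clarify how instruction 4 applies to a Grade 1 myocarditis hold when there has been no steroid taper.

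The choice of thresholds belongs to the sponsor, and none is proposed here. The cost is revised wording in Table 4 through a protocol amendment, with a communication to sites. Sample size, event targets and planned analyses do not change.

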**Dose modification and toxicity management of infusion-reactions related to pembrolizumab**

Pembrolizumab may cause severe or life-threatening infusion-reactions including severe hypersensitivity or anaphylaxis. Signs and symptoms usually develop during or shortly after drug infusion and generally resolve completely within 24 hours of completion of infusion. Dose modification and toxicity management guidelines on pembrolizumab associated infusion reaction are provided in [Table 5](#).

**Table 5 Pembrolizumab Infusion Reaction Dose Modification and Treatment Guidelines**

NCI CTCAE Grade	Treatment	Premedication at Subsequent Dosing
Grade 1 Mild reaction; infusion interruption not indicated; intervention not indicated	Increase monitoring of vital signs as medically indicated until the participant is deemed medically stable in the opinion of the investigator.	None
Grade 2 Requires therapy or infusion interruption but responds promptly to symptomatic treatment (eg, antihistamines, NSAIDs, narcotics, IV fluids); prophylactic medications indicated for $\leq 24$ h	
Stop Infusion.            Additional appropriate medical therapy may include but is not limited to:            IV fluids            Antihistamines            NSAIDs            Acetaminophen            Narcotics            Increase monitoring of vital signs as medically indicated until the participant is deemed medically stable in the opinion of the investigator.            If symptoms resolve within 1 hour of stopping drug infusion, the infusion may be restarted at 50% of the original infusion rate (eg, from 100 mL/h to 50 mL/h). Otherwise dosing will be held until symptoms resolve and the participant should be premedicated for the next scheduled dose.            Participants who develop Grade 2 toxicity despite adequate premedication should be permanently discontinued from further study drug treatment
	Participant may be premedicated 1.5h ( $\pm 30$ minutes) prior to infusion of pembrolizumab with: Diphenhydramine 50 mg po (or equivalent dose of antihistamine). Acetaminophen 500-1000 mg po (or equivalent dose of analgesic).
Grades 3 or 4 Grade 3: Prolonged (ie, not rapidly responsive to symptomatic medication and/or brief interruption of infusion); recurrence of symptoms following initial improvement; hospitalization indicated for other clinical sequelae (eg, renal impairment, pulmonary infiltrates) Grade 4: Life-threatening; pressor or ventilatory support indicated	
Stop Infusion.            Additional appropriate medical therapy may include but is not limited to:            Epinephrine**            IV fluids            Antihistamines            NSAIDs            Acetaminophen            Narcotics            Oxygen            Pressors            Corticosteroids            Increase monitoring of vital signs as medically indicated until the participant is deemed medically stable in the opinion of the investigator.            Hospitalization may be indicated.            **In cases of anaphylaxis, epinephrine should be used immediately.            Participant is permanently discontinued from further study drug treatment.
	No subsequent dosing
Appropriate resuscitation equipment should be available at the bedside and a physician readily available during the period of drug administration. For further information, please refer to the CTCAE v4.0 at http://ctep.cancer.gov		

### **Other allowed dose interruption for pembrolizumab**

Pembrolizumab may be interrupted for situations other than treatment-related AEs such as medical/surgical events or logistical reasons not related to study therapy. Participants should be placed back on study therapy within 3 weeks of the scheduled interruption, unless otherwise discussed with the Sponsor. The reason for interruption should be documented in the participant's study record. Imaging should not be delayed for delays in cycle treatment.

### **6.7 Part 2 – Crossover or Rechallenge Treatment After Recurrence**

The primary goal of the overall study is to compare RFS of pembrolizumab versus placebo, while ensuring access to pembrolizumab for all participants entering the study by allowing crossover/rechallenge after recurrence.

All participants will be unblinded at recurrence (Section 8.1.11) after Sponsor consultation and approval. The site should ensure data for disease recurrence is entered in the database prior to unblinding. Additionally, any AEs and/or SAEs should be reported and causality attributed in the database prior to unblinding. Participants will be encouraged to undergo full resection of the new lesion(s) if they experience local recurrence or have a biopsy if they experience unresectable or metastatic disease. Lymph node dissection should be undertaken per the recommendations of treating physician and surgeon.

For participants who decide to go on to Part 2 and otherwise meet criteria for crossover or rechallenge, resection or biopsy of unresectable or metastatic disease will be mandatory to confirm diagnosis. If biopsy is clinically contraindicated investigators should seek Sponsor review to start participant on Part 2 therapy. Participants should start Part 2 therapy within 4 weeks of recurrence. If participant requires longer time from surgical resection (eg, for recovery from surgery), Sponsor may be consulted to allow additional time before start of Part 2 therapy.

All participants who complete Part 1 study treatment with pembrolizumab or received placebo will be eligible for additional cycles of pembrolizumab if they meet Part 2 enrollment criteria listed below. Rechallenge/crossover is optional and is at the discretion of the Investigator upon notification of the Sponsor.

Participants assigned in the Part 1 initial treatment phase to the placebo arm who experience recurrence at any point during Part 1 therapy and follow-up and meet all crossover criteria will be offered crossover to pembrolizumab per dosing criteria in Section 4.3. Participants on the pembrolizumab arm during the initial phase of treatment who are greater than 6 months from last dose of pembrolizumab treatment and who experience a recurrence will be offered rechallenge with pembrolizumab per dosing criteria outlined in Section 4.3. Participants who have local recurrence, including local metastatic lymph nodes or distant metastases that are surgically resected may receive up to 17 cycles of therapy with pembrolizumab and participants with an unresectable local (regional metastatic lymph nodes, in-transit, satellite, and/or microsatellite metastases) or an unresectable distant recurrence may receive up to 35 cycles of therapy with pembrolizumab per Section 1.3.2.

All participants should have screening imaging within 28 days prior to C1D1 in Part 2 Crossover/Rechallenge phase. The Part 1 EOT scan can be used as baseline for Part 2 if done within 4 weeks of 1st dose in Part 2. Participants who have had surgical resection of lesion

captured on imaging must have a scan after surgery or radiation is complete to establish baseline imaging within 4 weeks prior to start of Part 2 therapy. Brain MRI must be obtained within 4 weeks prior to start of Part 2 treatment, unless contradicted; then CT may be acquired.

Disease recurrence/progression is confirmed by investigator (radiographically and/or by exam with subsequent biopsy) and RECIST 1.1/iRECIST will be used to identify disease progression in participants with metastatic/unresectable disease identified at the start of Part 2 therapy. Local recurrence should be documented with photo image.

Radiotherapy (palliative or adjuvant) is allowed prior to Part 2 (eg, post lymph node dissection radiotherapy when indicated). Radiotherapy has to be completed prior to first dose and complete wound healing is required prior to first dose. Radiotherapy is allowed during treatment in Part 2 as palliative therapy (treatment of pain, impending fracture, etc.) in participants with unresectable recurrence or metastatic disease. If surgery or radiotherapy other than described above is indicated while on Part 2 therapy Sponsor must be consulted.

All eligibility criteria from Part 1 Sections 5.1 and 5.2 remain valid and must be reconfirmed prior to enrollment into Part 2 of the study with the EXCEPTION of:

- Inclusion Criteria 2, 3, 4 and 5
- Exclusion Criteria 5, 6 and 11

Participants must also meet the following requirements for entry into Part 2:

- Participant must have experienced an investigator determined/confirmed disease recurrence radiographically and/or by exam with subsequent biopsy. Local recurrence must be documented with photo image. Participants will only be eligible for Part 2 treatment after the first recurrence. If a participant experiences a second recurrence, they will not be eligible for Part 2. Participants who are less than 6 months from their last Part 1 pembrolizumab dose at the time of recurrence are not eligible for Part 2 treatment.

Note: Cutaneous lesions and other superficial lesions detectable only by physical exam must be categorized as nontarget lesions for Part 2 of the study.

- No new anticancer treatment was administered after the last dose of Part 1 study treatment.
- Participant is continuing from Part 1 and has completed 17 cycles of pembrolizumab or any number of cycles with placebo with no delays in treatment  $\geq 12$  weeks. If a  $\geq 12$ -week treatment delay has occurred, Sponsor approval must be obtained before moving into Part 2 of the study.

Note: For any participant who is not able to complete the required 17 cycles of pembrolizumab or have  $\geq 12$ -week treatment delay on placebo arm, a notification to the Sponsor is required to determine if it would impact their eligibility for entry into Part 2.

- Surgical resection or biopsy of unresectable or metastatic disease completed within 4 weeks of first dose.

- Full resection of lesions or biopsy of unresectable or metastatic disease confirmed by site pathologist to be melanoma.

Note: If biopsy is clinically contraindicated, investigators should seek Sponsor review and approval to start participant on Part 2 therapy.

If participant is identified to have a thoracic lesion or lymph node suspicious for a recurrence (especially if solitary lesion), it is encouraged that a biopsy be performed to confirm metastatic melanoma versus another lung primary malignancy versus a nonmalignant lung disease (eg, sarcoidosis).

- Participants with focal or multifocal brain metastasis who are asymptomatic and do not require supraphysiologic steroid therapy per Section 5.2 are allowed in Part 2 of the study and may receive concurrent radiation to these lesions. Participants with leptomeningeal disease are not allowed to proceed to Part 2 of the study. A brain MRI is required to confirm presence of brain metastasis and evaluate for leptomeningeal disease prior to start of Part 2 treatment and if contraindicated a CT may then be used. Brain lesions are not to be recorded as target lesions but should be followed as nontarget lesions.
- ECOG performance status 0-2 in participants  $\geq 18$  years of age, LPS  $\geq 50$  for children up to and including 16 years of age, or KPS  $\geq 50$  for participants  $>16$  and  $<18$  years of age (Appendix 8).
- For Part 2 of the study, any participant who developed a severe hypersensitivity ( $\geq$ Grade 3) to any pembrolizumab excipients or pembrolizumab during Part 1 of the study will not be eligible for Part 2 therapy, as treatment in Part 1 was stopped secondary to an unacceptable AE.

Participants who discontinued study treatment during Part 1 due to documented disease recurrence on the pembrolizumab arm, unacceptable AEs, intercurrent illness that prevents further administration of treatment, investigator's decision to withdraw the participant, participant withdraws consent, participant requests to discontinue study treatment, pregnancy of the participant, noncompliance with study treatment, procedure requirements, or administrative reasons, are not eligible for Part 2.

